Phosphate, Low (mg/dL; mmol/L) >14 years of age 1 to 14 years of age <1 year of age	2.0 to < LLN 0.81 to < LLN 3.0 to <3.5 0.97 to <1.13 3.5 to <4.5 1.13 to <1.45	1.4 to <2.0 0.65 to <0.81 2.5 to <3.0 0.81 to <0.97 2.5 to <3.5 0.81 to <1.13	1.0 to <1.4 0.32 to <0.65 1.5 to <2.5 0.48 to <0.81 1.5 to <2.5 0.48 to <0.81	<1.0 <0.32 <1.5 <0.48 <1.5 <0.48
Potassium, High (mEq/L; mmol/L)	5.6 to <6.0 5.6 to <6.0	6.0 to <6.5 6.0 to <6.5	6.5 to <7.0 6.5 to <7.0	≥7.0 ≥7.0
Potassium, Low (mEq/L; mmol/L)	3.0 to <3.4 3.0 to <3.4	2.5 to <3.0 2.5 to <3.0	2.0 to <2.5 2.0 to <2.5	<2.0 <2.0

¹⁵ Use the applicable formula (ie, Cockcroft Gault in mL/min or Schwartz in mL/min/1.73m²).¹⁶ To convert a magnesium value from mg/dL to mmol/L, laboratories should multiply by 0.4114.

PARAMETER	GRADE 1 MILD	GRADE 2 MODERATE	GRADE 3 SEVERE	GRADE 4 POTENTIALLY LIFE- THREATENING
Sodium, High (mEq/L; mmol/L)	146 to <150 146 to <150	150 to <154 150 to <154	154 to <160 154 to <160	≥160 ≥160
Sodium, Low (mEq/L; mmol/L)	130 to <135 130 to <135	125 to <130 125 to <135	121 to <125 121 to <125	≤120 ≤120
Uric Acid, High (mg/dL; mmol/L)	7.5 to <10.0 0.45 to <0.59	10.0 to <12.0 0.59 to <0.71	12.0 to <15.0 0.71 to <0.89	≥15.0 ≥0.89

HEMATOLOGY				
PARAMETER	GRADE 1 MILD	GRADE 2 MODERATE	GRADE 3 SEVERE	GRADE 4 POTENTIALLY LIFE- THREATENING
Absolute CD4+ Count, Low (cell/mm³; cells/L) >5 years of age (not HIV infected)	300 to <400 300 to <400	200 to <300 200 to <300	100 to <200 100 to <200	<100 <100
Absolute Lymphocyte Count, Low (cell/mm³; cells/L) >5 years of age (not HIV infected)	600 to <650 0.600×10^9 to <0.650 $\times 10^9$	500 to <600 0.500×10^9 to <0.600 $\times 10^9$	350 to <500 0.350×10^9 to <0.500 $\times 10^9$	<350 $<0.350 \times 10^9$
Absolute Neutrophil Count (ANC), Low (cells/mm³; cells/L) ≥7 days of age 2 to 7 days of age ≤1 day of age	800 to 1,000 0.800×10^9 to 1.000 $\times 10^9$ 1,250 to 1,500 1.250×10^9 to 1.500 $\times 10^9$ 4,000 to 5,000 4.000×10^9 to 5,000 $\times 10^9$	600 to 799 0.600×10^9 to 0.799 $\times 10^9$ 1,000 to 1,249 1.000×10^9 to 1.249 $\times 10^9$ 3,000 to 3,999 3.000×10^9 to 3.999 $\times 10^9$	400 to 599 0.400×10^9 to 0.599 $\times 10^9$ 750 to 999 0.750×10^9 to 0.999 $\times 10^9$ 1,500 to 2,999 1.500×10^9 to 2.999 $\times 10^9$	<400 $<0.400 \times 10^9$ <750 $<0.750 \times 10^9$ <1,500 $<1.500 \times 10^9$
Fibrinogen, Decreased (mg/dL; g/L)	100 to <200 1.00 to <2.00 OR 0.75 to <1.00 x LLN	75 to <100 0.75 to <1.00 OR ≥0.50 to <0.75 x LLN	50 to <75 0.50 to <0.75 OR 0.25 to <0.50 x LLN	<50 <0.50 OR $<0.25 \times LLN$ OR Associated with gross bleeding
Hemoglobin¹⁷, Low (g/dL; mmol/L)¹⁸ ≥13 years of age (male only) ≥13 years of age (female only) 57 days of age to <13 years of age (male and female) 36 to 56 days of age (male and female) 22 to 35 days of age (male and female) 8 to ≤21 days of age (male and female) ≤7 days of age (male and female)	10.0 to 10.9 6.19 to 6.76 9.5 to 10.4 5.88 to 6.48 9.5 to 10.4 5.88 to 6.48 8.5 to 9.6 5.26 to 5.99 9.5 to 11.0 5.88 to 6.86 11.0 to 13.0 6.81 to 8.10 13.0 to 14.0 8.05 to 8.72	9.0 to <10.0 5.57 to <6.19 8.5 to <9.5 5.25 to <5.88 8.5 to <9.5 5.25 to <5.88 7.0 to <8.5 4.32 to <5.26 8.0 to <9.5 4.94 to <5.88 9.0 to <11.0 5.57 to <6.81 10.0 to <13.0 6.19 to <8.05	7.0 to <9.0 4.34 to <5.57 6.5 to <8.5 4.03 to <5.25 6.5 to <8.5 4.03 to <5.25 6.0 to <7.0 3.72 to <4.32 6.7 to <8.0 4.15 to <4.94 8.0 to <9.0 4.96 to <5.57 9.0 to <10.0 5.59 to <6.19	<7.0 <4.34 <6.5 <4.03 <6.5 <4.03 <6.0 <3.72 <6.7 <4.15 <8.0 <4.96 <9.0 <5.59
INR, High (not on anticoagulation therapy)	1.1 to <1.5 x ULN	1.5 to <2.0 x ULN	2.0 to <3.0 x ULN	≥3.0 x ULN
Methemoglobin (%) hemoglobin)	5.0 to <10.0%	10.0 to <15.0%	15.0 to <20.0%	≥20.0%

¹⁷ Male and female sex are defined as sex at birth.¹⁸ The conversion factor used to convert g/dL to mmol/L is 0.6206 and is the most commonly used conversion factor. For grading hemoglobin results obtained by an analytic method with a conversion factor other than 0.6206, the result must be converted to g/dL using the appropriate conversion factor for the particular laboratory.

PARAMETER	GRADE 1 MILD	GRADE 2 MODERATE	GRADE 3 SEVERE	GRADE 4 POTENTIALLY LIFE- THREATENING
PTT, High (not on anticoagulation therapy)	1.1 to <1.66 x ULN	1.66 to <2.33 x ULN	2.33 to <3.00 x ULN	≥3.00 x ULN
Platelets, Decreased (cells/mm ³ ; cells/L)	100,000 to <124,999 100.000×10^9 to <124,999 $\times 10^9$	50,000 to <100,000 50.000×10^9 to <100,000 $\times 10^9$	25,000 to <50,000 25.000×10^9 to <50,000 $\times 10^9$	<25,000 $<25.000 \times 10^9$
PT, High (not on anticoagulation therapy)	1.1 to <1.25 x ULN	1.25 to <1.50 x ULN	1.50 to <3.00 x ULN	≥3.00 x ULN
WBC, Decreased (cells/mm ³ ; cells/L)				
>7 days of age	2,000 to 2,499 2.000×10^9 to 2,499 $\times 10^9$	1,500 to 1,999 1.500×10^9 to 1,999 $\times 10^9$	1,000 to 1,499 1.000×10^9 to 1,499 $\times 10^9$	<1,000 $<1.000 \times 10^9$
≤7 days of age	5,500 to 6,999 5.500×10^9 to 6,999 $\times 10^9$	4,000 to 5,499 4.000×10^9 to 5,499 $\times 10^9$	2,500 to 3,999 2.500×10^9 to 3,999 $\times 10^9$	<2,500 $<2.500 \times 10^9$

URINALYSIS

PARAMETER	GRADE 1 MILD	GRADE 2 MODERATE	GRADE 3 SEVERE	GRADE 4 POTENTIALLY LIFE- THREATENING
Glycosuria (random collection tested by dipstick)	Trace to 1+ or ≤250 mg	2+ or >250 to ≤500 mg	>2+ or >500 mg	NA
Hematuria (not to be reported based on dipstick findings or on blood believed to be of menstrual origin)	6 to <10 RBCs per high power field	≥10 RBCs per high power field	Gross, with or without clots OR With RBC casts OR Intervention indicated	Life threatening consequences
Proteinuria (random collection tested by dipstick)	1+	2+	3+ or higher	NA

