11.5. Safety Analyses

No formal statistical testing of safety data is planned. Safety data will be analyzed descriptively.

Baseline for all safety parameters will be defined as the last evaluation done before the first dose of study vaccine.

AEs

The verbatim terms used in the CRF by investigators to identify AEs will be coded using the Medical Dictionary for Regulatory Activities (MedDRA). All reported AEs and events-related diary information (solicited local at injection site and systemic, and unsolicited) with onset within 28 days after each vaccination (ie, treatment-emergent AEs, and AEs that have worsened since baseline) will be included in the analysis. For each AE, the number and percentage of subjects who experience at least one occurrence of the given event will be summarized by group and/or by vaccine.

Summaries, listings, datasets, or subject narratives may be provided, as appropriate, for those subjects who die, who discontinue treatment due to an AE, or who experience a severe AE, an SAE, or an AESI.

Summaries and listings may be provided separately for AEs with onset outside the above defined timeframe and that were reported pre-dose at the moment of subsequent vaccinations.

Solicited local (at injection site) and systemic AEs will be summarized descriptively. The overall frequencies per vaccine group as well as frequencies according to severity and duration will be calculated for solicited AEs. In addition, the number and percentages of subjects with at least one solicited local (at injection site) or systemic AE will be presented. Frequencies of solicited and unsolicited AEs, separately for all and vaccination-related only, will be presented by System Organ Class and preferred term.

Clinical Laboratory Tests

Laboratory data will be summarized by type of laboratory test. Laboratory abnormalities will be determined according to a modified version of the DAIDS grading table, Version 2.0 ([Attachment 1](#)), and in accordance with the normal ranges of the clinical laboratory. Laboratory abnormalities will be tabulated per treatment group and/or per vaccine.

Vital Signs

The percentage of subjects with values beyond pre-specified limits (see [Attachment 1](#)) will be summarized.

Physical Examination

Physical examination findings will not be tabulated separately. Clinically relevant findings will be reported as AE and will be tabulated and listed as AEs. BMI will be calculated using the recording of height at screening.

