Blood Pressure Abnormalities¹ Hypertension (with the lowest reading taken after repeat testing during a visit) ≥18 years of age	140 to <160 mmHg systolic OR 90 to <100 mmHg diastolic	≥160 to <180 mmHg systolic OR ≥100 to <110 mmHg diastolic	≥180 mmHg systolic OR ≥110 mmHg diastolic	Life-threatening consequences in a participant not previously diagnosed with hypertension (eg, malignant hypertension) OR Hospitalization indicated
<18 years of age	>120/80 mmHg	≥95th to <99th percentile + 5 mmHg adjusted for age, height, and gender (systolic and/or diastolic)	≥99th percentile + 5 mmHg adjusted for age, height, and gender (systolic and/or diastolic)	Life-threatening consequences in a participant not previously diagnosed with hypertension (eg, malignant hypertension) OR Hospitalization indicated
Hypotension	No symptoms	Symptoms corrected with oral fluid replacement	Symptoms AND IV fluids indicated	Shock requiring use of vasopressors or mechanical assistance to maintain blood pressure
Tachycardia^b - beats per minute	101 - 115	116 - 130	> 130	ER visit or hospitalization for arrhythmia
Bradycardia^a - beats per minute	50 - 54	45 - 49	< 45	ER visit or hospitalization for arrhythmia
Cardiac Ischemia or Infarction Report only one	NA	NA	New symptoms with ischemia (stable angina) OR New testing consistent with ischemia	Unstable angina OR Acute myocardial infarction
Heart Failure	No symptoms AND Laboratory or cardiac imaging abnormalities	Symptoms with mild to moderate activity or exertion	Symptoms at rest or with minimal activity or exertion (eg, hypoxemia) OR Intervention indicated (eg, oxygen)	Life-threatening consequences OR Urgent intervention indicated (eg, vasoactive medications, ventricular assist device, heart transplant)

^b Modification of DAIDS toxicity table consistent with FDA guidance "Toxicity Grading Scale for Healthy Adult and Adolescent Volunteers Enrolled in Preventive Vaccine Clinical Trials, September 2007

Hemorrhage (with significant acute blood loss)	NA	Symptoms AND No transfusion indicated	Symptoms AND Transfusion of ≤ 2 units packed RBCs indicated	Life-threatening hypotension OR Transfusion of >2 units packed RBCs (for children, packed RBCs >10 cc/kg) indicated
--	----	---------------------------------------	--	---

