## 5.2. Clinical Laboratory Tests

Any clinically relevant lab value measured from signing of the ICF onwards must be recorded on the adverse event page of the CRF and are analyzed as AE. The data will be summarized by the type of laboratory test.

In case a laboratory test result is *censored* (no numeric value is available, but only a verbatim term) then a numeric value will be imputed by a value preceding or exceeding the cut-off value with one unit. (<x: subtract 1 unit from x, >x: add 1 unit to x)

*Toxicity grades* will be determined according to the DAIDS Grading list (see also [APPENDIX 1](#)). In case no toxicity grades are defined for a test, the abnormalities (above/below normal range) will be used. In determining toxicity grades, the following rules are applied:

- worst grades/abnormalities are determined over the whole observational period for each trial phase separately, including all post-baseline measurements of that phase.
- The abnormalities ‘abnormally low’ and ‘abnormally high’ are considered equally important, i.e. if a subject has as well an abnormally low as an abnormally high value post-baseline, both abnormalities are shown in the tables. (This means that the sum of the percentages can be more than 100%)
- Note: as the grading scale for some parameters in the grading table has some gaps (zones where no toxicity grade definition exists), laboratory results falling in these zones will be allocated to the adjacent worst-case grade.
- If a lab value falls within the grading as specified in the grading table but also within the (local) lab normal limits, the value is considered as normal

Definition emergent: An abnormality (toxicity grade or abnormality based on normal ranges) will be considered emergent in a particular phase if it is worse than the baseline (baseline = prior very first vaccination). If the baseline is missing, the abnormality is always considered as emergent. A shift from ‘abnormally low’ at baseline to ‘abnormally high’ post baseline (or vice versa) is also emergent.

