## 5.3. Vital Signs

### 5.3.1. Definitions

Vital sign measurements will be performed at the time points indicated in the Time and Events Schedule (see CTP). Following parameters will be summarized:

- Temperature (°C)
- Blood Pressure: systolic/diastolic (mmHg)
- Pulse rate (bpm)

For definition of emergent refer to section [5.2](#).

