### 5.3.2. Analysis methodology

Any clinically relevant vital signs occurring from signing of the ICF onwards must be recorded on the adverse event page of the CRF and are analyzed as AEs. Tabulations of the parameters per period following vaccination will be provided. All findings will be listed by subject and by time point. Tabulations of the worst emerging abnormalities will be performed for parameters if applicable (see grading on [APPENDIX 1](#)).

Physical examination data will only be listed.

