**APPENDIX 1: LABORATORY, VITAL SIGNS AND ABNORMALITY GRADINGS**

PARAMETER	LABORATORY a			
	GRADE 1 MILD	GRADE 2 MODERATE	GRADE 3 SEVERE	GRADE 4 POTENTIALLY LIFE-THREATENING
HEMATOLOGY				
Absolute Neutrophil Count (ANC) (cells/L) c	800 x 10  – 1.000 x 10 	0.600 x 10  – 0.799 x 10 	0.400 x 10  – 0.599 x 10 	<0.400 x 10 
Hemoglobin (Hgb) (HIV NEGATIVE ONLY)				
Male	10.0 – 10.9 g/dL	9.0 – 9.9 g/dL	7.0 – 8.9 g/dL	<7.0 g/dL
Female	9.5 – 10.4 g/dL	9.4 – 8.5 g/dL	8.4 – 6.5 g/dL	<6.5 g/dL
Platelets, decreased b	100.000 x 10  – 124.999 x 10  /L	50.000 x 10  – 99.999 x 10  /L	25.000 x 10  – 49.999 x 10  /L	<25.000 x 10  /L
WBC, decreased b	2.000 x 10  – 2.500 x 10  /L	1.500 x 10  – 1.999 x 10  /L	1.000 x 10  – 1.499 x 10  /L	<1.000 x 10  /L
CHEMISTRIES				
ALT (SGPT)	1.25 – 2.5 x ULN	2.6 – 5.0 x ULN	5.1 – 10.0 x ULN	>10.0 x ULN
AST (SGOT)	1.25 – 2.5 x ULN	2.6 – 5.0 x ULN	5.1 – 10.0 x ULN	>10.0 x ULN
Creatinine	1.1 – 1.3 x ULN	1.4 – 1.8 x ULN	1.9 – 3.4 x ULN	≥ 3.5 x ULN
URINALYSIS				
Hematuria	6-9 RBC per high power field	≥10 RBC per high power field	Gross, with or without clots or with RBC casts	Transfusion indicated
Proteinuria, random collection	1+	2+	3+ or higher	NA

aThis list is restricted to the laboratory parameters collected in this study for which a DAIDS 2.0 grading is available. Only ranges applicable for adults are reported. For a complete list refer to the CTP appendix 1

bThe decrease is a decrease from baseline

cIf ANC is not available the values will be derived by from the ratio Neutrophils/Leucocytes

VITAL SIGNS a					
PARAMETER	UNIT	GRADE 1	GRADE 2	GRADE 3	GRADE 4
Temperature	°C	≥38.0 - ≤38.5	≥38.6 - ≤39.2	≥39.3 - ≤39.9	≥40.0
Hypertension					
Systolic Blood Pressure	mmHg	≥140 - ≤159	≥160 - ≤179	≥180	NA
Diastolic Blood Pressure	mmHg	≥90 - ≤99	≥100 - ≤109	≥110	NA
Hypotension	mmHg	NA	NA	NA	NA
Pulse rate					
Tachycardia	bpm	≥101-≤115	≥116 - <130	>130	NA
Bradycardia	bpm	≥50 - ≤54	≥45 - ≤49	<45	NA

aDAIDS 2.0 grading, see also CTP appendix 1

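### SAP Appendix 1 leaves a pulse of exactly 130 bpm ungraded, although Attachment 1 makes it Grade 2, and omits Attachment 1's rule for which blood-pressure reading is graded

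*Protocol*

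**What the plan says.** Protocol 11.5 promises one vital-sign summary: "The percentage of subjects with values beyond pre-specified limits", with the limits taken from Attachment 1. In the Cardiovascular table of Attachment 1, tachycardia is Grade 1 at 101 - 115 bpm, Grade 2 at 116 - 130 and Grade 3 above 130. Adult hypertension has mmHg bands and a condition in the row label: it is graded "with the lowest reading taken after repeat testing during a visit".

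SAP Appendix 1 gives its source in a footnote to the vital-signs table: "DAIDS 2.0 grading, see also CTP appendix 1". It lists tachycardia Grade 1 as ≥101 - ≤115, Grade 2 as ≥116 - <130 and Grade 3 as >130. The hypertension rows carry the mmHg bands only.

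SAP 5.3.2 states "Tabulations of the parameters per period following vaccination will be provided" and "Tabulations of the worst emerging abnormalities will be performed for parameters if applicable". SAP 5.3.1 takes one thing from the laboratory section: "For definition of emergent refer to section" 5.2.

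**The concern.** A grading table that names its source should return the same grade as that source for every recordable value. If it does not, the percentage promised in Protocol 11.5 and the SAP tabulation can disagree on the same data. An adverse event graded by the investigator from Attachment 1 can also carry a different grade from the same measurement in the vital-signs table.

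Two departures are at stake. The pulse bound is a definite mismatch on the page. The missing blood-pressure condition is an omission. It matters only if more than one reading per time point is stored: a programmer would then have no instruction on which to grade, and a transient high reading that settles on repeat could be counted as an abnormality that Attachment 1 would not recognise.

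**Working it through.** **Inputs.** Grade bands from Protocol Attachment 1 (Cardiovascular) and SAP Appendix 1 (Vital Signs). Only Grades 1 to 3 are compared, because Grade 4 for these parameters is defined in Attachment 1 by clinical consequences and not by a measured value. The plan states no figure to reproduce.

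**Step 1: compare the bands value by value.** Each whole-number value was graded under both tables.

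| Parameter | Range checked | Values graded differently |
|---|---|---|
| Pulse, tachycardia bands | 30-220 bpm (191 values) | 1: 130 bpm |
| Systolic pressure | 60-259 mmHg | 0 |
| Diastolic pressure | 30-159 mmHg | 0 |

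The bradycardia bands are the same in both tables. At 130 bpm, Attachment 1 has 116 ≤ 130 ≤ 130, so Grade 2. In the SAP, 130 < 130 is false and 130 > 130 is false, so there is no grade.

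**Step 2: can another SAP rule rescue the value?** SAP 5.2 has a gap rule: "laboratory results falling in these zones will be allocated to the adjacent worst-case grade". It is worded for laboratory results, and 5.3.1 imports only the definition of emergent. If it were borrowed anyway, the adjacent worse grade is Grade 3, which still differs from Attachment 1.

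**Step 3: who is affected?** With 130 ungraded, a subject's worst grade in a period is too low only if at least one reading is exactly 130 and no other reading is 116 or more. A reading of 116-129 gives Grade 2 anyway, and a reading above 130 gives Grade 3 under both tables. With the gap rule borrowed, a subject whose highest reading is exactly 130 moves from Grade 2 to Grade 3. The documents do not show how many such readings exist.

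**Step 4: the blood-pressure condition.** Take an illustrative first reading of 146 mmHg, repeated at 128 in the same visit.

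- Attachment 1: min(146, 128) = 128, below 140, no grade.
- If all stored readings were graded: max(146, 128) = 146, Grade 1.
- If no repeat is stored: both rules use 146, and the grade is the same.

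A difference therefore needs a stored repeat and a decision to use every reading. The protocol allows one repeat of out-of-range vital signs at screening, for eligibility (9.1.3). The second measurement on vaccination days is the planned post-dose one (9.1.4). No confirmatory repeat is scheduled after baseline.

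**Step 5: how far the answer depends on repeats.** An illustration was run on assumed inputs, none of them from the documents: systolic mean and between-subject SD of 118 and 11 or 125 and 13 mmHg, within-visit SD 5 or 8, 3 or 4 visits, and a share q of readings of 140 or more repeated once. A subject counts if any visit's maximum (or, under Attachment 1, minimum) is 140 or more. The excess of the maximum rule over the minimum rule was:

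- q = 0: 0 points in every scenario.
- q = 0.5: from 6.8 − 5.2 = 1.6 to 32.7 − 26.5 = 6.2 percentage points.
- q = 1: from 6.8 − 3.3 = 3.5 to 32.7 − 18.4 = 14.3 percentage points.

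These runs ignore the comparison with baseline that the SAP's definition of emergent requires. They show sensitivity to q and are not an estimate for this trial.

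**The case against.** A reader might infer that the SAP grades the worst reading within a visit and so over-counts hypertension. The documents do not say this. SAP 5.3.2 takes the worst abnormality and tabulates by period, and a period spans several visits. Worst across visits is compatible with lowest after repeat within each visit. The sentence that would support the stronger reading, "worst grades/abnormalities are determined over the whole observational period for each trial phase separately, including all post-baseline measurements of that phase", is a laboratory rule that the vital-signs section does not import. Nothing shows that the database holds more than one reading per time point. This part of the objection stands, and it reduces the blood-pressure point to an unstated detail.

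A reader might also infer that such noise would mask a difference between vaccine and placebo. No calculation here contains a vaccine effect or an arm comparison, and safety is descriptive with no formal testing. SAP 5.3.2 also lists all findings by subject and time point and analyses clinically relevant ones as adverse events, so a high reading that settled on repeat would be visible if stored.

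Third, the pulse slip concerns one value and gives no support to a claim about blood pressure. Left ungraded, it under-counts. That is fair. It does not remove the mismatch: the bound contradicts the table the SAP cites, and the other bounded pulse rows close with ≤, which suggests a slip of one symbol.

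Finally, vital signs are collected only to Week 72, and SAP section 1 says the Week 72 analysis is done and will not be rerun. This stands, and it limits the practical action to a data check.

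**Conclusion.** The pulse bound is wrong as written: exactly 130 bpm is Grade 2 in Attachment 1 and has no grade in SAP Appendix 1. This rests on the text alone. Its reach is one whole-number value.

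The missing blood-pressure condition is a real omission but a conditional one. Its effect is zero unless post-baseline repeat readings are stored and all of them are used. The documents establish neither, so no over-count is shown and no number of affected subjects can be given.

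Both are minor. The tables are descriptive, no decision rule in the SAP depends on them, and the relevant outputs already exist. Those outputs may have been produced under SAP version 1.0, which is not among the documents reviewed, so whether they used the faulty bound has to be checked.

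**What to change.** 1. In SAP Appendix 1, change tachycardia Grade 2 to ≥116 - ≤130, matching Attachment 1.
2. In SAP 5.3.2, add a sentence to this effect: *for blood pressure, the value graded at a time point follows Attachment 1 (the lowest reading after repeat testing), with pre-dose and post-dose time points kept separate and the same rule applied at baseline; the worst grade per period is then taken over these values.*
3. Query the vital-signs data for any pulse equal to 130 and any time point with more than one blood-pressure reading, and confirm which bound and which reading the Week 72 programs used. If a table entry would change, annotate the report.

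The cost is one symbol, one sentence and a short query. No new data and no rerun are needed unless the query finds an affected entry.

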APPENDIX A: TOTAL BILIRUBIN TABLE FOR TERM AND PRETERM NEONATES

PARAMETER	GRADE 1 MILD	GRADE 2 MODERATE	GRADE 3 SEVERE	GRADE 4 POTENTIALLY LIFE- THREATENING
Total Bilirubin¹⁹, High (mg/dL; μmol/L) ²⁰				
Term Neonate²¹				
<24 hours of age	4 to <7 68.4 to <119.7	7 to <10 119.7 to <171	10 to <17 171 to <290.7	\geq 17 \geq 290.7
24 to <48 hours of age	5 to <8 85.5 to <136.8	8 to <12 136.8 to <205.2	12 to <19 205.2 to <324.9	\geq 19 \geq 324.9
48 to <72 hours of age	8.5 to <13 145.35 to <222.3	13 to <15 222.3 to <256.5	15 to <22 256.5 to <376.2	\geq 22 \geq 376.2
72 hours to <7 days of age	11 to <16 188.1 to <273.6	16 to <18 273.6 to <307.8	18 to <24 307.8 to <410.4	\geq 24 \geq 410.4
7 to 28 days of age (breast feeding)	5 to <10 85.5 to <171	10 to <20 171 to <342	20 to <25 342 to <427.5	\geq 25 \geq 427.5
7 to 28 days of age (not breast feeding)	1.1 to <1.6 x ULN	1.6 to <2.6 x ULN	2.6 to <5.0 x ULN	\geq 5.0 x ULN
Preterm Neonate²¹				
35 to <37 weeks gestational age	Same as for Total Bilirubin, High, Term Neonate (based on days of age).	Same as for Total Bilirubin, High, Term Neonate (based on days of age).	Same as for Total Bilirubin, High, Term Neonate (based on days of age).	Same as for Total Bilirubin, High, Term Neonate (based on days of age).
32 to <35 weeks gestational age and <7 days of age	NA	NA	10 to <14 171 to <239.4	\geq 14 \geq 239.4
28 to <32 weeks gestational age and <7 days of age	NA	NA	6 to <10 102.6 to <171	\geq 10 \geq 171
<28 weeks gestational age and <7 days of age	NA	NA	5 to <8 85.5 to <136.8	\geq 8 \geq 136.8
7 to 28 days of age (breast feeding)	5 to <10 85.5 to <171	10 to <20 171 to <342	20 to <25 342 to <427.5	\geq 25 \geq 427.5
7 to 28 days of age (not breast feeding)	1.1 to <1.6 x ULN	1.6 to <2.6 x ULN	2.6 to <5.0 x ULN	\geq 5.0 x ULN

¹⁹ Severity grading for total bilirubin in neonates is complex because of rapidly changing total bilirubin normal ranges in the first week of life followed by the benign phenomenon of breast milk jaundice after the first week of life. Severity grading in this appendix corresponds approximately to cut offs for indications for phototherapy at grade 3 and for exchange transfusion at grade 4.

²⁰ A laboratory value of 1 mg/dL is equivalent to 17.1 μ mol/L.

²¹ Definitions: Term is defined as \geq 37 weeks gestational age; near term, as \geq 35 weeks gestational age; preterm, as <35 weeks gestational age; and neonate, as 0 to 28 days of age.

